8 STUDY OBJECTIVES AND ENDPOINTS

8.1 Primary objective

To evaluate the moderate and severe diarrhea attack rate after challenge with wild type enterotoxigenic *E. coli* (ETEC) strain E24377A

8.1.1 Primary endpoint

Moderate and severe diarrhea, as defined by ≥ 4 grade 3-5 stools **or** > 400 grams of grade 3-5 stools passed within a rolling 24-hour period, deemed attributable to ETEC.

Diarrhea episodes or ETEC symptoms beginning any time after challenge through 120 hours post-challenge may contribute toward the primary endpoint and will be followed to resolution. The end of a diarrheal episode occurs when a subject does not pass any grade 3-5 stool within 24 hours. An adjudication committee will be used to judge if the diarrhea is attributable to ETEC and determine if a subject meets the primary endpoint by considering individual data as described in the adjudication charter.

Stool grading criteria: grade 1 = firm, formed; grade 2 = soft but still formed; grade 3 = thick liquid; grade 4 = thin liquid; grade 5 = clear or translucent, watery

8.2 Secondary objectives

- To further evaluate the clinical features of the challenge with wild type ETEC strain E24377A
- To evaluate the safety of the challenge with wild type ETEC strain E24377A

8.2.1 Secondary Clinical endpoints

- Severe diarrhea defined as ≥ 6 grade 3-5 stools or > 800 g of grade 3-5 stools passed within a rolling 24-hour period.
- ETEC disease severity: 3-component disease score (total score) utilizing objective signs, subjective symptoms and stool output [31].
- Incidence of diarrhea (≥ 2 grade 3-5 stools in a 24-hour period) of any severity.
- Total weight of grade 3-5 stools passed per subject over the 120-hour observation period.
- Number of grade 3-5 stools per subject over the 120-hour observation period.
- Occurrence of other ETEC Disease-specific events (malaise, loss of appetite, headache, chills, fever, nausea, abdominal pain, abdominal cramps, myalgia, arthralgia, urgency of defecation, vomiting and lightheadedness).
- Self-assessment of ETEC illness impact on daily activity at Day 6.

- Time (relative to challenge) to the first grade 3-5 stool of the first diarrhea episode.
- Time (relative to challenge) to meeting the primary endpoint (time of the stool that meets the criteria for at least moderate diarrhea).
- Requirement of early (prior to Day 6) antibiotic treatment.
- Requirement of IV fluids.
- Maximum 24-hour grade 3-5 stool output (weight).
- Maximum number (24-hour) of grade 3-5 stools.

8.2.2 Secondary Microbiology endpoint

- Qualitative shedding of the E24377A challenge strain post-challenge (positive or negative)

8.2.3 Secondary Safety endpoints

- Adverse events leading to study withdrawal
- Serious adverse events (SAEs) occurring during the 6 months of the study (from the time of challenge)

8.3 Exploratory Objective(s)

8.3.1 Exploratory immunogenicity objective

To evaluate immunogenicity of the challenge with wild type enterotoxigenic *E. coli* (ETEC) strain E24377A

8.3.1.1 Exploratory immunogenicity endpoints that may be conducted

- Serum IgA and IgG antibody seroconversion (≥ 2 -fold increase over baseline to challenge strain specific antigens LT, CS1, CS3 in serum) from baseline prior to challenge and post-challenge. In addition, ≥ 4 -fold increase may be explored.
- Increases in serum IgA measurements utilizing Antibody in the Lymphocyte Supernatant (ALS) assay in response to LT, CS1, and CS3.
- Increases in Memory B cell measurements utilizing Antibody in the Lymphocyte Supernatant (ALS) assay.
- Whole blood for transcriptomics.
- Increases in Fecal IgA levels to LT, CS1, CS3 from baseline prior to challenge and post-challenge.
- Biomarker assessments to measure intestinal inflammation in stool (e.g. calprotectin, neopterin, myeloperoxidase).
- Biomarker assessments to measure systemic inflammation in serum (e.g. C-reactive protein, Intestinal Fatty Acid binding protein).
- Fecal microbiome assessment.

Specific collection days will be detailed in the Manual of Procedures.

8.3.2 Exploratory microbiology objective

To evaluate the level of quantitative fecal shedding (colony forming units per gram of stool) of the E24377A challenge strain post-challenge

8.3.2.1 Exploratory microbiology endpoints

- Number of colony forming units (cfu) per gram of stool of the E24377A challenge strain on Days 2 and 4 after challenge

9 INVESTIGATIONAL PLAN

This is an open label study with the aim to estimate the incidence of moderate and severe diarrhea among participants challenged with 4×10^9 cfu of the *E. coli* E24377A strain. [REDACTED]

The study will be conducted at one site; the Center for Immunization Research, Johns Hopkins Bloomberg School of Public Health in Baltimore, Maryland, United States.

Up to 30 (minimum 25) subjects will be enrolled and challenged with approximately 4×10^9 cfu of the *E. coli* E24377A strain.

Overall description of study design

The study will consist of three study periods: screening, inpatient period and outpatient follow-up. Subjects will be evaluated for study eligibility during the screening period. After provision of written informed consent, subject eligibility for study entry will be assessed. Subjects who have been assessed to be eligible for the study, based on screening evaluations, will be admitted to the in-patient unit on Day -1, the day before E24377A administration, for study orientation and to be monitored for any signs and symptoms of illness. At baseline (Day 1), subjects who remain eligible and are willing to participate will be enrolled in the study and receive a single administration of E24377A.

Subjects may remain in the in-patient unit until they meet discharge criteria, see Section 9.4.8.2. Routine discharge is scheduled for Day 9, dependent upon 2 consecutive negative stool culture results. During the in-patient period, subjects will be examined daily for signs and symptoms of ETEC illness. Vital signs will be measured at least 3 times daily starting on Day 1, and postural blood pressure and pulse will be measured as needed. All stools will be collected and evaluated, weighed, and graded by the study staff. Up to 3 stools and/or rectal swabs collected each day will be cultured.

If the subject develops any symptom suggestive of diarrhea, they will be encouraged to drink liquids. If a subject vomits or is unable to consume an adequate volume of liquids, then intravenous (IV) fluids may be administered.

In order to reduce the risk of secondary infection after discharge, all subjects will receive a 3-day course of antibiotics. The subject will begin a 3-day course of ciprofloxacin 500 mg by mouth twice daily (or azithromycin 500 mg by mouth daily for three days, or amoxicillin 500 mg by mouth three times daily for three days if the subject was allergic to or unwilling to take

ciprofloxacin per the PI discretion) on the morning of Day 6, or sooner if the subject has met the criteria for early antibiotic treatment (see Section 9.4.8.2).

Subjects will be discharged from the in-patient unit if determined eligible for discharge (2 stools negative for the challenge organism by culture, having received at least 2 doses of antibiotics, with improvement or resolution of symptoms). Subjects who meet the criteria for early antibiotic treatment, may be discharged from the in-patient unit prior to Day 9.

After discharge from the in-patient unit, all subjects will attend the scheduled follow-up visit/contact on an out-patient basis on Day 29 (physical visit) and Day 180 (phone).

The analyses for the exploratory endpoints may continue after the study database has been locked.

The timing and frequency of study visits and assessments are presented in the schedule of events in Table 1.

Table 1. Schedule of Events (Subject Visit Schedule and assessments)

	Study Specific Screen	Inpatient period										Out-patient visit	Phone call
Study Day	Scr -60 to -2	-1	1	2	3	4	5	6	7	8	9	29	180
Informed Consent and Comprehension Test	X												
Demographics	X												
Inclusion/Exclusion Criteria	X	X	X										
Medical History	X	X											
Functional Bowel Survey	X												X
COVID-19 Test		X											
Full Physical Exam	X	X											
Focused Physical Exam			X	X	X	X	X	X	X	X	X	(X) ¹	
Vital Signs ²	X	X	X	X	X	X	X	X	X	X	X		
Serology (HIV, HBsAg, and HCV)	X ³												
CBC w/diff	X	X ⁴											
Clinical Chemistry	X	X ⁴											
ABO Type	X												
IgA deficiency screen	X ³												
Serum HCG Pregnancy Test ⁵	X	X											
Urine Drug Screen	X												
Urine Pregnancy Test ⁵			(X)										X
Enrollment			X										
E24377A challenge			X										
Prior and concomitant medications	X	X	X	X	X	X	X	X	X	X	X		
Interim Medical Interview ⁶			X	X	X	X	X	X	X	X	X		X
AE			X	X	X	X	X	X	X	X	X		
SAE/AESI			X	X	X	X	X	X	X	X	X		X
Start Antibiotic therapy								X ⁷					
Stool collection for weighing and grading ⁸			X	X	X	X	X	X	X	X	(X)		
Stool culture ⁹			X	X ¹⁰	X	X ¹⁰	X	X	X	X	(X)		
Fecal samples for exploratory immunogenicity endpoints		X	(X) ¹¹	X	X	X	X	X	X	X	(X)		X
Blood Samples for exploratory Immunogenicity endpoints		X	(X) ¹¹		X	X				X			X

Whole blood for ALS/Memory B Cells/PaxGene		X	(X) ¹¹			X			X		X		
ETEC Impact on ADLs							X						
Planned Discharge										X ¹²			
Follow-Up Telephone Contact													X
Study Completion													X

Note: (X) denotes optional event or procedure

Note: Procedures to be performed at an unscheduled visit are described in section 9.5.6.6. Procedures to be performed in case of an early termination are described in section 9.5.6.8.

¹ Physical exam on Day 29 optional per PI discretion.

² Pulse, sitting, lying or standing blood pressure and temperature will be measured at least 3 times daily starting on Day 1. In addition, postural blood pressure and pulse will be measured if suspicion or evidence of hypovolemia (based on assessment by clinician). Vital signs may be measured more frequently if the subject is ill.

³ Must be collected from Day -30 to Day -2.

⁴ Hematology and clinical chemistry will be performed at Day -1 if not performed within the previous 7 days.

⁵ Serum HCG pregnancy tests will be performed for people of child-bearing potential. Urine HCG will be done if serum results from admission day (Day -1) are not available.

⁶ During the inpatient and outpatient phases of the study, the interview will be used to update baseline medical history, monitor safety, and to confirm ongoing eligibility.

⁷ Subjects meeting the criteria for early antibiotic treatment per the discretion of an investigator may start this treatment prior to Day 6.

⁸ Weighing and grading ends once participant has two consecutive ETEC negative cultures, unless there is a clinical indication to continue.

⁹ Once a participant has two stools in a row negative for ETEC, their stools will no longer be cultured.

¹⁰ Quantitative stool cultures (cfu per gram of stool) will be collected on Days 2 and 4.

¹¹ To be collected before challenge if not taken on Day -1.

¹² Anticipated discharge date. Participant may be discharged earlier or later depending on when they meet discharge criteria and per PI discretion.

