9.5.7 Appropriateness of measurements

Standard safety assessment methods are used in this study and are very similar to procedures performed in all previously conducted clinical studies in which the E2477A challenge strain was used.

The purpose of the current study is to estimate the incidence of moderate and severe diarrhea among participants challenged with 4×10^9 cfu of the *E. coli* E24377A strain. This dose is planned to be used in a subsequent randomized, double-blind, placebo-controlled phase 3 vaccination and CHIM study. In order to meet this objective, all stools will be collected during in-patient period from immediately after E24377A administration on Day 1 through meeting discharge criteria and examined, weighed, and graded by the study staff using standard criteria.

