Subjects meeting the criteria for early antibiotic treatment per the discretion of an investigator may start this treatment prior to Day 6.

Weighing and grading ends once subject has two consecutive ETEC negative cultures, unless there is a clinical indication to continue.

Quantitative stool cultures (cfu per gram of stool) will be collected on Days 2 and 4.

To be collected before challenge if not taken on Day -1.

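### The two-negative-culture stop on stool weighing, grading and culture has no time floor, contradicts the body text, and can end measurement inside the 120-hour endpoint window

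*Protocol*

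**What the plan says.** Three footnotes carry the stop rule:

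- Protocol Table 1, footnote 8, on weighing and grading: "Weighing and grading ends once participant has two consecutive ETEC negative cultures, unless there is a clinical indication to continue".
- SAP Table 1, footnote 8, the same rule: "Weighing and grading ends once subject has two consecutive ETEC negative cultures, unless there is a clinical indication to continue".
- Protocol Table 1, footnote 9, on culture: "Once a participant has two stools in a row negative for ETEC, their stools will no longer be cultured". It has no exception.

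The body text says otherwise. Protocol 9.5.7 has it that "all stools will be collected during in-patient period from immediately after E24377A administration on Day 1 through meeting discharge criteria". Protocol sections 9, 9.5.3.1 and 9.5.6.2.3 have all inpatient stools collected, weighed and graded, with no culture-based stop. Section 9.5.6.3 ends collection only when the discharge criteria are met. SAP 2.6.1 has every inpatient stool collected, with its time, weight and grade recorded. SAP 2.7.1 plans culture on each inpatient day and mentions no two-negative stop.

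The endpoints need the full window. Protocol 8.1.1: "Diarrhea episodes or ETEC symptoms beginning any time after challenge through 120 hours post-challenge may contribute toward the primary endpoint". Section 8.2.1 adds totals over the same period, such as: "Total weight of grade 3-5 stools passed per subject over the 120-hour observation period".

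**The concern.** The primary endpoint is a count or weight of loose stools in a rolling 24-hour period, so it can be read from the stool log only while stools are being weighed and graded. The footnotes allow that to stop on culture results alone, at any time after challenge. Early negative cultures do not show that a subject is past risk if illness can begin two or three days after challenge.

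The attack rate at this dose is the number the study exists to supply to the planned efficacy study. A subject who falls ill after measurement has stopped could be recorded as a non-case. Stopping culture also removes evidence that the adjudication committee may want when it judges attribution to ETEC.

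**Working it through.** **1. What ends stool measurement, by place**

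| Place | Ends when | Minimum time | Antibiotics needed |
|---|---|---|---|
| Protocol and SAP footnote 8 (weighing, grading) | two consecutive negative cultures, unless a clinical indication | none | no |
| Protocol footnote 9 (culture) | two negatives in a row | none | no |
| Protocol 9.5.6.3 and 9.5.7 | discharge criteria met | implied, see step 2 | at least 2 doses |
| Protocol 9, 9.5.3.1, 9.5.6.2.3; SAP 2.6.1 | no culture-based stop | – | – |

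The discharge criteria (protocol 9.4.8.2) are two negative stools, at least two antibiotic doses, and absent or improved symptoms. The footnotes keep only the culture part.

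**2. Timing**

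Protocol 9.5.6.2.3 places Day 6, when routine antibiotics start, 5 days after challenge: 5 × 24 = 120 h. A subject not treated early therefore cannot meet the two-dose criterion before about 120 h, so the body text protects the window for that subject. The footnotes do not.

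The earliest trigger depends on sampling. Section 9 of the protocol says "Up to 3 stools and/or rectal swabs collected each day will be cultured", and 7.3.2 allows both discharge negatives to come from one day. On Day 1, section 9.5.6.2.2 saves only grade 3-5 stools for culture; routine sampling starts on Day 2. Two Day 2 samples could meet the rule on paper. No culture turnaround time is given. If the stop took effect at 24 or 36 h, 120 − 24 = 96 h or 120 − 36 = 84 h would remain. Those figures are upper bounds.

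**3. Onset against the window**

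Protocol 7.2 gives a median time to diarrhea of 25 h. Table 3 gives group means of 26, 29, 29.6 and 47 h for lot 0807, with a range of 7 to 84 h in the group of 16 (13 ill).

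As an illustration, assume log-normal onset among cases with median 25 h. The log-SD inferred from the range is ln(84/7)/3.336 = 2.485/3.336 = 0.745, where 3.336 is the expected range of 13 standard normal values. The share of eventual cases starting after time t is 1 − Φ[(ln t − ln 25)/SD]:

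| t | SD 0.745 | SD from 0.5 to 0.9 |
|---|---|---|
| 24 h | 52% | 52–53% |
| 36 h | 31% | 23–34% |
| 48 h | 19% | 10–23% |
| 72 h | 8% | 2–12% |

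This says how much illness is still to come. It does not say how many of those subjects would first give two consecutive negatives.

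**4. Effect on the estimate**

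The SAP 2.4.1 intervals reproduce with exact Clopper-Pearson limits: 15/25 gives (0.387, 0.789) and 18/25 gives (0.506, 0.879). Starting from 18 true cases in 25, with k of them unmeasured and counted as non-cases:

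| k | Estimate | 95% CI |
|---|---|---|
| 0 | 72% | 0.506, 0.879 |
| 1 | 68% | 0.465, 0.851 |
| 2 | 64% | 0.425, 0.820 |
| 3 | 60% | 0.387, 0.789 |

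Per missed case the loss is 1/25 = 4.0 points, or 1/30 = 3.3 points. Three missed cases turn the SAP's 72% scenario into its 60% scenario.

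**5. Whether the analysis would show it**

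SAP 2.5.4.1 and 2.5.4.2 censor subjects without an event at 120 h; the Table 15 note uses discharge if that comes first. Neither uses the end of stool measurement. The Full Analysis Set (SAP 3.3) keeps challenged subjects with available data, SAP 3.5 imputes nothing, and the Listing 6 mock-up has no field for when measurement stopped. An inpatient whose stools were no longer measured is therefore handled as observed to 120 h.

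Culture summaries are affected too. SAP Table 19 counts only subjects with a culture result that day, so dropping subjects after two negatives raises later positive percentages. Two negatives by Day 3 would also cancel the quantitative culture planned for Day 4.

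**The case against.** The strongest reply is that the footnote is not absolute. Weighing continues on a clinical indication, and new loose stools in an inpatient would plausibly be one. Subjects are interviewed and examined daily, the unit has medical staff around the clock, and section 9.4.8.2 needs stool output to guide oral fluids, early antibiotics and IV fluids. The primary endpoint is also a committee decision: SAP 2.5.4.1 expressly allows a subject whose measured stools fell below threshold to be called a case. Several body sections require full measurement, and the documents give neither a culture turnaround time nor any rate of two negatives followed by illness.

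Most of this stands, and it limits the likely loss. Three gaps remain. The exception is undefined, and nothing says how stools passed before it is invoked are recovered. It does not extend to culture, so weighing could resume in an ill subject while culture does not. The body text that points the other way is itself the contradiction: staff cannot follow both.

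An instruction to weigh and culture everyone to 120 h would also fail. Subjects treated early may leave once they meet discharge criteria, and section 9.5.6.7 sends no stool cultures after early discharge. The remedy has to be limited to inpatients.

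**Conclusion.** The point holds as a contradiction over when measurement stops, in which one of the competing rules can bias the primary estimate. Under the footnotes, measurement can end inside the 120-hour window and before late-onset illness. Unmeasured stools cannot create a case, so the resulting error in the attack rate is downward: 4.0 points per missed case at n = 25, 3.3 at n = 30. The number of missed cases is unknown, and the figures for one to three are assumptions.

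A reader might infer more than the documents support:

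- That any two negatives stop measurement outright. They must be consecutive, and weighing and grading have an exception.
- That 84 to 96 h would typically be lost. That needs Day 2 negatives with near-immediate results, and on Day 1 the section text cultures only loose stools.
- That every unmeasured case becomes a non-case. The committee can still call one; the more direct exposure is the unadjudicated endpoint and the stool totals.
- That unmeasured hours are set to zero by rule. The SAP says only that missing values are not imputed. It gives no rule for shortened observation, so a sum of recorded stools would look complete.

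How much lost cultures would affect attribution depends on the adjudication charter, which is not among the documents.

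**What to change.** Reword protocol Table 1 footnotes 8 and 9 and SAP Table 1 footnote 8 so that, while a subject remains inpatient:

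- every stool is weighed and graded through at least 120 h after challenge, and to the end of any open episode, whatever the culture results;
- at least one stool or swab per day is cultured through 120 h;
- the two-negative stop applies only after that.

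This brings the footnotes into line with protocol 9, 9.5.3.1, 9.5.6.2.3, 9.5.6.3 and 9.5.7 and SAP 2.6.1 for the endpoint window. Leave the discharge criteria and early-discharge procedures as they are.

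In the SAP, flag any subject whose stool observation ended before 120 h, including through early discharge, as incomplete for the 120-hour totals.

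The cost is three reworded footnotes, one SAP flag, and a small amount of extra weighing and culture in subjects already on the unit.

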9.1.1 Stopping rules/Discontinuation Criteria

Scandinavian Biopharma AB has the right to close the study at any time, although this should occur only after consulting involved parties. The IRB and the FDA must be informed. Events that may trigger premature termination of the study include, but are not limited to: safety reasons, results of any interim analysis, non-compliance with the protocol, change in development plans for the subsequent planned vaccination and challenge study, slow recruitment and poor quality data.

9.1.2 Internal Safety Review Committee (iSRC)

There will be no iSRC for this study.

9.2 Rationale for study design, doses and control group

For this pre-study and the planned CHIM study involving the ETVAX® vaccine, the E24377A ETEC strain is considered to be the best suited as (a) there is a fair amount of experience with E24377A (third most commonly used challenge strain [22]), (b) the disease severity score is predominantly moderate [23] and (c) the time to diarrhea is with a median of 25 hours post-

challenge also intermediate compared to common ETEC challenge strains (e.g. 47 hours for H10407 and 13 hours for B7A) and, therefore well suited for a 5-10 day in-house challenge period [23].

The 0807 GMP lot of the ETEC E24377A strain has been used in previous CHIM studies to assess the efficacy of other candidate ETEC vaccines [18, 24]. The *E. coli* ETEC strain E24377A was first used in human challenge studies in the early 1980s [25]. Table 2 below presents a summary of the previous use of the selected challenge strain E24377A (*E. coli* O139: H28; LT⁺ ST⁺; CS1+ CS3) in CHIM studies. Challenge doses ranging from 6×10^8 to 4×10^9 were used with overall diarrheal attack rates around 80% and moderate to severe ETEC illness around 60-81%. The pre-study to precede the proposed CHIM study is planned to estimate the incidence of moderate and severe diarrhea among participants challenged with 4×10^9 cfu of the *E. coli* E24377A strain.

No serious adverse events occurred in any of the studies listed in Table 2.

Table 2. Strain E24377A used in CHIM studies

Publication	Number Placebo subjects	Challenge Dose (cfu)	GMP status for challenge strain	Diarrhea Attack rate (%)	Comment
Levine 1984 [25]	14	5×10^8	Research grade	64%	-
Levine 1986 [26]	6	5×10^8	Research grade	100%	-
Tacket 1994 [27]	10	3×10^9	Research grade	100%	-
Tacket 1999 [28]	10	1×10^8	Research grade	30%	-
McKenzie 2007 [18]	20	6×10^8	Lot 0807 cGMP grade	100% [75%*]	LT patch vaccine trial
McKenzie 2008 [24]	10	7×10^8	Lot 0807 cGMP grade	80% [60%*]	Challenge dose-finding trial
	10	4×10^9		80% [70%*]	
	16	3×10^9	Lot 0807 cGMP grade	81% [81%*]	PTL-003 live-attenuated ETEC vaccine trial

* Attack rate of moderate to severe ETEC illness (moderate to severe diarrhea or mild diarrhea with moderate to severe GI symptoms) [18, 24]

E24377A was, in the early 1980s, isolated from a traveler returning from Egypt with an ETEC diarrheal illness [18], and it shares the CS3 and LT antigens with one of the *E. coli* strains the ETVAX® vaccine but is of a different O and H antigen type. E24377A harbors two colonization factors, CS1 and CS3, as well as the enterotoxins LT and ST. Since not only the colonization factors (CS1, CS3) and toxins (LT, ST) are expressed but also other common virulence factors (data on file from bioinformatic analysis performed [REDACTED]) E24377A is considered a representative strain for conducting a CHIM study involving the ETVAX® vaccine.

The CS1+CS3 CF combination of virulence factors are well-represented in field isolates and contribute to virulence/infectivity/disease severity throughout the world. They are seen in ETEC strains causing disease in both adults and children globally [19]. A detailed analysis of the genes

encoding CS1, CS3, LT and ST in E24377A show that they are identical or highly similar (>99%) in comparison to the respective genes in other CS1+CS3 ETEC strains.

Provoked diarrheal illnesses after challenge in studies with the same preparation (lot 0807) of strain E24377A are presented in Table 3. The cGMP grade preparation of the ETEC strain E24377A (lot 0807) has been used in previous CHIM studies [18, 24], and triggered at doses of $6 \times 10^8 - 4 \times 10^9$ moderate to severe ETEC illness of 60-81% (Table 2).

Table 3. Clinical experience in naïve subjects challenged with ETEC E24377A (Lot 0807 cGMP grade)

Type of study	CHIM trial McKenzie 2007 [18]	Challenge dose-finding McKenzie 2008 [24]		CHIM trial McKenzie 2008 [24]
No Subjects ¹	N=20	N=10	N=10 ²	N=16
Challenge dose (cfu)	6×10^8	7×10^8	4×10^9	3×10^9
Attack rate (overall)	20 (100%)	80%	80%	13 (81%)
Attack rate (moderate/severe ETEC illness) ³	15 (75%)	6 (60%)	7 (70%)	13 (81%)
Time to illness (mean hours)	29 h	47 h	26 h	29.6 h (7 -84)
Stool volume (mean ml or g)	585 (0 – 1821) ⁴	740	1400	1009 (0 – 5085)
Mean No loose stools	4.7 (0 – 12) ⁴	5	8	6.9 (0 -25)
No subjects with a key symptom ⁵	NA	NA	NA	8 (50%)
Early antibiotics given	12/15 (80%)	NA	NA	8 (50%)
IV fluid treatment needed	6/15 (40%)	NA	NA	NA

NA = not available in publications; cfu = colony forming units

¹ Data in this table is from only placebo recipients or unimmunized subjects in the trials cited

² 10 subjects in this group is a composite of 5 subjects given 4.9×10^9 cfu and 5 subjects given 3.1×10^9 cfu of 24377A

³ Moderate to severe ETEC illness includes mild diarrhea with moderate to severe GI symptoms

⁴ During 0-48h after challenge

⁵ Moderate or severe nausea, vomiting, anorexia, or abdominal pain/cramps

